Interims computations of sample size will be performed to ensure the study maintains 70% power to detect a 10% difference in the primary endpoint with use of the appropriate statistical test. An interim computation will occur when ½ of the cases have completed the protocol. The interim computations 1) will involve only interim estimates of standard deviations of interest along with their corresponding 95% confidence intervals, 2) will be blind to whether “Group 1” or “Group 2” was to the VR-aided method, and 3) will not reveal to the surgeons or patients any information about magnitudes of group differences. If power is deemed inadequate, the sample size will be adjusted in both the number of Control Cases and Intervention Cases accordingly. This will be accomplished by repeating the sample size calculation described in Section IVd with data from the ongoing study. Adjustments to sample size are anticipated to be relatively small in relation to the large overall sample size.

c. Control Cases

The set of control cases (“*Control Cases*”) will be all operations:

- That meet the criteria set forth in Section II above;
- Are performed by the surgeons participating in the study;
- Which occur after commencement of the study, until such time as the calculated number of Control Cases (as discussed more fully below) have been completed; and
- Which are identified as Control Cases as discussed in subsection (d) below.

Sample size for Intervention Cases has been calculated based on the methodology described above, and Control Case sample size shall be calculated using a 1:1 group ratio.

d. Randomization, blinding, and sample size calculation

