Eligible subjects identified from the medical record will be those who are 1) scheduled to undergo RALPN surgery, 2) willing to consent to the surgery being performed by one of the four surgeons participating in the study, and 3) willing to be assigned by randomization to a preparation method (VR-aided or control). Each case will be assigned to one of the two preparation methods by a randomization procedure that is stratified by surgeon (four separate surgeon-specific randomization schedules.) Each surgeon-specific randomization schedule will be prepared using permuted blocks of size 2; i.e., each 2-patient block will be some permutation of {VR-aided, Control}. Thus, each surgeon’s cases will be randomized in a 1:1 ratio. Use of permuted blocks thus avoids any confounding of preparation method with temporal trends (e.g., trend due to a learning curve.) Approximately 20 sequentially numbered opaque sealed envelopes (SNOSEs) will be prepared for each individual surgeon, each containing the treatment assignment for one case, and will provided to the Research Coordinator. The treatment code will remain concealed inside the envelope until

the moment the case is ready to be prepared. Patients, personnel gathering data from the video review, and statistician will be blinded. Control and intervention groups identifiers will be known only to the research personnel opening the sealed envelope for random group assignment and extracting patient data from the electronic medical record.

We calculated the sample size based on our pilot data of the total operative time, which shows an effect size of 0.44 regarding the difference of total operative time between VR-aided and control groups. We took the within-surgeon correlation to be 0.3. We use data from the most-of-interest variable (aka total operative time). To account for the within-cluster correlation, we adopted the sample size calculation method proposed in [1]. We took three values of within-cluster correction ($\rho = 0.3, 0.5, 0.7$) to consider low/moderate/high levels of within cluster correlation. In order to account for multiple endpoints and some other unpredictable factors, we propose to raise the sample size by 15%. We selected $\rho=0.3$ given the wide variation in case complexity seen in our pilot study, which drastically limited within-cluster clustering. Our target sample size using this method is 78 patients.

	$\rho = 0.3$	$\rho = 0.5$	$\rho = 0.7$
Before adjustment	34	39	47

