After 15% adjustment	39	45	54

[1] Diggle, P. J., Heagerty, P., Liang, K. Y., and Zeger, S. L. (2002). Analysis of Longitudinal Data. New York: Oxford University Press.

e. Statistical Model

Baseline values (means, standard deviations and proportions) will be tabulated together with corresponding confidence intervals (CIs) for each primary endpoint in both the Control Cases and Intervention Cases based on relevant historical data. For primary endpoints of various operative times, the nonparametric Wilcoxon signed rank test will be utilized to calculate the sample size needed to have 70% power to detect a 10% difference. False Discovery Rate (FDR) control will be enforced by using Benjamini-Hochberg procedure at the level of 5% in order to account for multiple testing issue.

Statistical analysis will include standard comparison of baseline endpoints between VR-aided and control groups with the appropriate statistical tests depending on the type of outcomes. For continuous outcomes (e.g. various operative times), the nonparametric Wilcoxon signed rank test will be used for comparison, which does not rely on the normality assumption. For binary outcomes (e.g. Mortality), Fisher's exact test will be used. P-values of all tests will be reported. The threshold of rejecting null hypothesis will be chosen at the conventional level of 0.05. Tests fail to be rejected will be reported as inconclusive. To study the adjusted difference between case/control group, we will also use generalized linear mixed model to regress the endpoint variables on Surgical and Clinical covariates listed in **Exhibit A**, where random effects will be imposed on surgeon clusters. Depending on the type of outcome, the linear mixed model (for continuous outcome) or the logistic mixed model (for binary outcome) will be used. To ensure normality, the continuous outcome will be Box-Cox transformed. In the regression analysis, we also use model diagnosis tools, such as QQ-plots to ensure various assumptions for the regression model are met. In

addition, to test the reliability of our model, we will also perform sensitivity analyses by splitting data into training and test set and perturb various assumptions (such as normality assumption and the Box-Cox transformation) in the regression model and inspect how well the results can be reproduced. The repeated measure ANCOVA will be used to test the adjusted difference between case/control groups.

V. SURGEON SURVEYS

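### Section IV.e checks the adjusted model by a training/test split of about 78 patients, with no ratio or comparison measure; at this size the outcome depends largely on which split is drawn

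*Combined protocol and SAP*

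**What the plan says.** Section IV.e (Statistical Model) compares the arms first by unadjusted tests. It then fits a linear or logistic mixed model with the Exhibit A covariates and random surgeon effects, with continuous outcomes Box-Cox transformed. To judge that model's reliability the section states: "we will also perform sensitivity analyses by splitting data into training and test set". The same sentence adds a second action, perturbing assumptions such as normality and the Box-Cox transformation, and says the analysts will "inspect how well the results can be reproduced". QQ-plots are planned as well.

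The section does not state the split ratio, the number of splits, whether the split is stratified by surgeon and arm, which quantity is compared, or what counts as agreement.

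On size, section IV.d says: "Our target sample size using this method is 78 patients". Patients are randomised 1:1 in blocks of two within each of four surgeons. Exhibit A ticks eight patient-level covariates for this operation (resident and fellow involvement, age, sex, Charlson index, nephrometry score, mass size, laterality), plus surgeon experience and surgeon identifier.

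**The concern.** A training/test split is mainly a tool for judging prediction when there are many observations. Here the quantity of interest is one randomised treatment effect, estimated in a trial sized for 70% power with all its patients. A test set of 16 to 39 patients must support the same arm effect, surgeon terms and covariates, so its estimate is far less precise than the one it is meant to check.

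Disagreement between the parts would then mostly reflect small numbers, and agreement would be weak evidence of a sound model. Because ratio, split and comparison measure are open, they could also be settled after the results are known. A favourable split could be shown, or an unfavourable one could cast doubt on a sound result.

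**Working it through.** **The plan's own figure.** Section IV.d gives 34 per arm before inflation at correlation 0.3. 34 × 1.15 = 39.1, taken as 39, and 2 × 39 = 78. That step reproduces. The starting 34 does not follow from the stated inputs: the clustered formula needs a cluster size that is not given, and a size of 3 returns 34.0, 42.5 and 51.0 against the plan's 34, 39 and 47. That is a separate matter; 78 is used below as the planned size.

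**Inputs from the documents.**
- Effect (IV.d): "which shows an effect size of 0.44 regarding the difference of total operative time between VR-aided and control groups".
- Correlation (IV.d): "We took the within-surgeon correlation to be 0.3".
- Level (IV.e): "The threshold of rejecting null hypothesis will be chosen at the conventional level of 0.05".
- Power (IV.b): "70% power to detect a 10% difference in the primary endpoint".

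**Assumed, because not stated.** Two-sided testing; ratios 50/50, 70/30 and 80/20 (test sets of 39, about 23 and about 16); covariates explaining 30% of within-surgeon variance.

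**Step 1: power in half the sample.** At 70% power the standardised effect is 1.960 + 0.524 = 2.484. In half the patients it is 2.484 × √0.5 = 1.757, and power is Φ(1.757 − 1.960) = 42%. Both halves are significant in 0.42² = 18% of trials.

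**Step 2: precision of the test-set estimate.** With 4 surgeon terms and 8 covariates unrelated to arm, the information on the arm effect is roughly proportional to n(n − 12)/(n − 4) if the part stays balanced within surgeon, and to n − 12 if it is drawn at random. For all 78 (balanced) it is 78 × 66/74 = 69.6.

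| Test set | Balanced: information, SE ratio | Random: information, SE ratio | Simulated SE ratio |
|---|---|---|---|
| 39 | 39 × 27/35 = 30.1, √(69.6/30.1) = 1.5 | 27, 1.6 | about 1.5 |
| 23 | 23 × 11/19 = 13.3, √(69.6/13.3) = 2.3 | 11, 2.5 | about 2.4 |
| 16 | 16 × 4/12 = 5.3, √(69.6/5.3) = 3.6 | 4, 4.2 | about 3.7 |

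At 80/20 with surgeon as a fixed effect, the test set has 16 − 4 − 8 − 1 = 3 residual degrees of freedom.

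**Step 3: what a reader would see when the full result is significant.** Simulated trials with a true effect of 0.44 SD, kept only if significant on all 78:

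| Split | Test set significant, eight covariates | Test set significant, one covariate | Parts do not both have the correct sign |
|---|---|---|---|
| 50/50 | 46% | 55% | 1–2% |
| 70/30 | 20% | 31% | – |
| 80/20 | 9% | 20% | 10–22% |

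**Step 4: dependence on the draw.** With 100 random splits of each significant trial (eight covariates), the typical 5th to 95th percentile range of test-set estimates, as a multiple of the full-data estimate, is 0.3 to 1.7 (50/50), −0.2 to 2.2 (70/30) and −1.5 to 3.4 (80/20). At 50/50, in 94% of trials between 10% and 90% of the splits are significant.

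**Step 5: a different measure.** If agreement means that the training estimate lies in the test-set 95% interval, an unadjusted simulation at 0.44 SD gives agreement in 86%, 92% and 95% at 50/50, 70/30 and 80/20. The check becomes easier to pass as the test set shrinks, because the interval widens.

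**The case against.** The strongest reply is that the plan contains no pass/fail rule. A reader might infer that a real effect will usually fail this check and be reported as not reproducible. The documents do not support that: they ask only for inspection, set no significance requirement in either part, and give no rule by which the split overturns or relabels a result. The only label, inconclusive, belongs to tests that do not reject. By sign, a real effect that is significant on all 78 agrees in about 78–99% of trials, depending on split and model. This stands.

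Three further readings go beyond the text:
- That the split is meant to probe normality or Box-Cox. That is the job of the separate perturbation step.
- That there will be a single arbitrary split. The number of splits is simply not stated.
- That the split breaks the balance within surgeon. Stratified splitting would be compatible with the wording. If the split were simple random, a 16-patient test set would lack an arm or a whole surgeon in 59% of draws, but the plan does not say so.

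Part of the low significance rate also comes from the trial, not the split: unadjusted power at 0.44 with 39 per arm is only about 48–49%. Conditioning on a significant full result, as in step 3, limits this but does not remove it. Finally, the 30% covariate share is assumed. Varying it from 0 to 50% in a one-covariate model moves 50/50 test-set significance from 49% to 62%.

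What the reply leaves untouched is the imprecision in steps 2 and 4, which needs no significance criterion.

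**Conclusion.** The concern holds in a limited form. The plan names a weak method for its stated purpose and leaves every element that would give it meaning undefined. With about 78 patients the test-set effect is 1.5 to 3.7 times less precise than the full-data effect in an eight-covariate model, so the impression of reproducibility will depend largely on the split drawn. Significance in the test set would be an unsuitable measure: it is reached in about 46–55% of already significant trials at 50/50 and in 9–20% at 80/20.

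The split is a sensitivity analysis of the adjusted model. The unadjusted comparisons do not depend on it, and nothing here shows that the trial's main result would be wrong. The numbers rest on the plan's 0.44 and 0.3, two-sided testing, the assumed split ratios and the assumed 30% covariate share. The degrees-of-freedom count and the SE approximation also treat surgeon as a fixed effect; a random surgeon effect would cost somewhat fewer degrees of freedom in a small test set.

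**What to change.** In section IV.e, replace the training/test split by checks that use all patients:

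1. A bootstrap confidence interval for the arm effect from the adjusted model, resampling patients within surgeon and arm (about 78/8 ≈ 10 per cell), with the number of resamples stated in advance.
2. The arm estimate and confidence interval with each surgeon left out in turn.

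Report these beside the main adjusted estimate and interval, with no significance criterion. Keep the QQ-plots and the planned perturbation of assumptions, made concrete as the same model on raw, log and rank scales. Units differ across those scales, so compare direction and relative precision.

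The cost is SAP wording, a few lines of code and minor extra analysis. With four surgeons the leave-one-out estimates are descriptive only. If the team prefers to keep a split, the SAP should at least fix beforehand the ratio, the number of repeated splits, stratification by surgeon and arm, and the measure compared.

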Using Virtual Reality (VR) Models for Preoperative Planning

NCT03334344

9/12/2017

Title of Study: Using Virtual Reality (VR) Models for Preoperative Planning
Technology Provider: Ceevra, Inc.
Device Name: Ceevra Reveal

I. BACKGROUND AND RATIONALE

a. Introduction

The purpose of the proposed study is to assess whether surgeons who view virtual reality (VR) models of their patients' anatomy during the preoperative planning process develop a better understanding of such anatomy, resulting in more efficient operations and improved patient care.

b. Study justification and design

The typical approach for a surgeon planning an operation such as a robotic assisted laparoscopic partial nephrectomy (RALPN) involves reviewing a traditional CT scan or MRI, which is comprised of a series of 2D black and white slices that the surgeon then views from multiple angles to form a "mental 3D reconstruction" of the kidney, the mass, and any important structures near the kidney. Surgeons are continuously looking for ways to improve upon this planning process and enhance patient care, and one emerging area for such improvement is the use of advanced imaging technologies.

In this study, three-dimensional (3D) models of the patient's anatomy will be created by technology provider Ceevra, Inc. ("*Ceevra*") using software that converts preexisting CT scans and MRIs into 3D models and then displays those models in a virtual reality format (the "*VR Models*") through mobile phones or tablets. The software utilized by Ceevra to perform these functions, Clarity Reveal, is classified as a medical device, product code LLZ (Image Processing System) (the "*Device*"). On August 3, 2017, Ceevra received 510(k) clearance from the FDA (registration number K171356) for the use of the Device for preoperative surgical planning. On July 20, 2018, Ceevra received additional 510(k) clearance from the FDA (registration number K173274) for the use of the Device to display the VR Models during the operations as well. The indications for use are as follows:

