Ceevra Reveal 2.0 is intended as a medical imaging system that allows the processing, review, analysis, communication and media interchange of multi-dimensional digital images acquired from CT or MR imaging devices. It is also intended as software for preoperative surgical planning, and as software for the intraoperative display of the aforementioned multi-dimensional digital images. Ceevra Reveal 2.0 is designed for use by health care professionals and is

intended to assist the clinician who is responsible for making all final patient management decisions.

In the VR Models, each primary anatomical structure (for example, the kidney, the kidney mass, the main renal vein and the main renal artery) is assigned a unique color and texture to help surgeons identify these structures. The kidney is made translucent to enable the surgeons to see the depth of the mass as well as its size and shape. The VR Models will be accessed by surgeons through their mobile phones, and then viewed through a generally commercially available VR headset to allow for a more immersive viewing experience.

The surgeons involved in this study will view both the VR Models and the original CT/MRI during their surgical planning process. The surgeons may also view the VR Models and the original CT/MRI during the operation itself. The researchers will then compare the results of the operations in which both the VR Models and the CT/MRIs are viewed to the results of operations in which the same surgeons viewed only the CT/MRIs. As more fully detailed Exhibits A and C below, endpoints to be evaluated include intraoperative times (specifically, tumor localization, tumor resection, reconstruction), blood loss, clamp time, patient hospital stay, margins and complications.

The researchers hypothesize that viewing the VR Models during the preoperative planning process may enable the participating surgeons to develop a better understanding of their patients' anatomy, which in turn may have the following benefits:

- Improved surgical efficiency, for example reduced operating time and associated time under anesthesia; reduced blood loss; and reduced ischemia; and
- Improved patient recovery process, including reduced post-operative discomfort and shortened hospital stay.

c. Prior similar studies

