In 2016, [name] undertook a limited study at UCLA Health pursuant to an IRB-approved quality assurance waiver. Using several off-the-shelf software applications, [name] created virtual reality models from CT scans for 30 upcoming RALPN cases. During the preoperative planning process for those cases, the surgeons viewed both the source CT scan as well as the virtual reality model. Using multivariate statistical analysis, the results of those cases were compared to 30 RALPN cases performed by same surgeons in which only the underlying CT/MRI was viewed during the preoperative planning process. The endpoints and results of this study were as follows:

- Operative time (30% reduction when VR Model used during preoperative planning)
- Blood loss (51% reduction when VR Model used during preoperative planning)
- Ischemia (25% reduction when VR Model used during preoperative planning)
- Patient hospital stay (20% more likely to be discharged by post-op Day 2 when VR model used during preoperative planning)
- Case complexity (27% higher average Nephrometry score for cases in which VR model used during preoperative planning)

The researchers in this study seek to expand significantly on the above described study by including new primary endpoints and utilizing VR Models created by Ceevra with the Device.

d. Relevant Literature and Data

The prior study described above represents the first study to demonstrate a definitive advantage in surgical planning using virtual reality models. Furthermore, the study demonstrated that the surgeons in the study were more willing to perform surgery on complex tumors with the VR models.

Previous studies using 3D printed models have shown subjective improvement in operative planning when surgeons were surveyed after viewing the models (Zhang et al, 2016), but review of this technique is limited (Soliman et al, 2015). VR models provide an increased level of detail beyond what is seen in 3D printed models, since the fidelity of 3D printing limits detail.

Advanced imaging technologies such as CT or MRI guided biopsy also differ markedly from this study, as they rely on fusion of multiple imaging modalities as well as the use of intraoperative imaging.

II. CASE TYPES INVOLVED IN STUDY

- a. Robotic assisted laparoscopic partial nephrectomy (RALPN)
- b. Exclusions:
 - i. Cases involving subjects who are minors, pregnant or require an authorized representative for informed consent

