- a. **Post-Operative Surveys:** A short survey will be administered to the surgeon following completion of each Intervention Case (“*Post-Operative Surveys*”). The survey will include questions regarding the Primary Endpoints (as measured on a Likert-type scale), and the helpfulness of the VR Models during case planning. No PHI will be reflected or gathered in these surveys.
- b. **Surgeon Experience Surveys:** Surgeon experience surveys will be administered with each participating surgeon two times during study: The first one after the surgeon has completed 5 Intervention Cases, and the second one at the completion of the study (“*Surgeon Experience Surveys*”). No PHI will be gathered or reflected in these surveys. Initial list of questions set forth on **Exhibit B**.
- c. **Purpose.** The Post-Operative Surveys and Surgeon Experience Surveys will be used by the researchers to further assess whether and to what degree the VR Models:
 - i. Impact the surgeons’ understanding of their patients’ anatomy;
 - ii. Impact the surgeons’ confidence in their preoperative plans;
 - iii. Impact the surgeons’ accuracy in their preoperative plans;
 - iv. Impact the surgeons’ efficiency in their intraoperative execution;
 - v. Are perceived as particularly beneficial in cases with any specific anatomical characteristics;
 - vi. Are perceived as particularly beneficial to any specific surgery types; and
 - vii. Are perceived as more or less helpful when viewed in VR format as opposed to regular 3D format.

VI. HOSPITAL PARTICIPANTS AND RESPONSIBILITIES

- a. **Principal Investigator (PI)**
 - i. Overall point person for study.
 - ii. Coordinates support for study with other participants, including Research Coordinator and surgeon users.
- b. **Research Coordinator (“RC”):**
 - i. Identify, collect and manage:
 - The CTs and MRIs from which the VR Models will be created by Ceevra
 - Data regarding Control Cases (“**Control Case Data**”) and Intervention Cases (“**Intervention Case Data**”)
 - ii. Deidentify each source CT/MRI using deidentifying software (or ensures that Radiology deidentifies the image prior to delivery to the RC); deliver the deidentified image to Ceevra along with a unique identifier.
 - iii. Coordinate with surgeon users to ensure that both the VR model and the underlying CT/MRI are reviewed prior to operation.

- iv. Assist with administration of the Post-Operative Surveys and the Surgeon Experience Surveys.
- c. **Surgeon Users.** Key activities:

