 - i. Identify upcoming cases for which VR models will be created.
 - ii. Oversee receipt of informed consents from all patients participating in the study.
 - iii. Provide the mobile phone used for viewing the VR models (Ceevra to provide VR headsets, 1 per surgeon user).
 - iv. Before each Intervention Case operation, review the source CT/MRI and then review the associated VR Model for purposes of case planning.
 - v. Participate in Post-Operative Surveys and Surgeon Experience Surveys.

VII. PROJECT IMPLEMENTATION

- a. **Protocol for Case Data.** Control Case Data and Intervention Case Data will be extracted from the EHR system, and the Post-Operative Surveys. It will be tracked via two forms maintained within REDCap which requires unique user IDs and passwords:
 - i. First form will include patient information (listed below) and a unique identifier. This form will be accessible by researchers only.
 - 1. Medical Record Number (MRN)
 - 2. Surgeon Number
 - 3. CT/MRI ID #
 - 4. Operation Date
 - 5. Unique Identifier
 - ii. Second form will include the unique identifier and outcomes data, but no PHI. See **Exhibit C** for example of data fields (partial nephrectomy cases). This form will be accessible by both site and Ceevra researchers.
- b. **Protocol for Control and Intervention Cases and Randomization**
 - i. For Intervention Cases, surgeons will be provided with the VR model to view prior to the operation in addition to the CT or MRI scan as described below. For Intervention Cases, surgeons will also have the option to view the VR model during the operation in addition to the CT or MRI scan. For Control Cases, surgeons will view the CT or MRI scan only.
 - ii. Subjects will be identified from the medical record as scheduled to undergo one of the surgery types being included in the study, with the surgery being performed by one of the surgeons participating in the study. Subjects will be randomized at a 1:1 ratio to either control or intervention groups using block randomization.
- c. **Protocol for VR Models**
 - i. PI/RC identifies upcoming Intervention Cases, based on the above criteria and the results of randomization, for which VR models are to be created.
 - ii. PI/RC obtains source CT/MRI for such cases, deidentifies the same using deidentifying software (or ensures that Radiology deidentifies the image prior to delivery to the PI/RC), delivers it to Ceevra along with a unique identifier.

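### The trial compares access to the VR model before and, optionally, during surgery, so it does not support a conclusion about preoperative planning alone

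*Combined protocol and SAP*

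**What the plan says.** The title of the study names preoperative planning. Section I.a gives the purpose as finding out whether surgeons who look at VR models "during the preoperative planning process develop a better understanding of such anatomy, resulting in more efficient operations and improved patient care". The hypothesis in Section I.b puts the mechanism at the same stage: "viewing the VR Models during the preoperative planning process may enable the participating surgeons to develop a better understanding". The bi-weekly review in Section VIII.c also describes VR cases as those where the model was used in planning.

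The intervention is wider than that. Section I.b states: "The surgeons may also view the VR Models and the original CT/MRI during the operation itself". Section VII.b.i repeats this for Intervention Cases, where "surgeons will also have the option to view the VR model during the operation", and sets the comparator: "For Control Cases, surgeons will view the CT or MRI scan only".

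Viewing the model before surgery is required in every Intervention Case and is followed up by the coordinator (Sections VI.b, VI.c and VII.c). Viewing it in theatre is left to the surgeon.

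**The concern.** The stated question is whether planning with the model makes operations more efficient. The arms differ in two respects: the model is seen beforehand, and it may be seen again during the operation.

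The primary endpoints ticked for partial nephrectomy in Exhibit A are hilum dissection, tumor localization, tumor resection, reconstruction and total operative time. All are measured while a surgeon may be consulting the model. A look at the model in theatre could shorten localization or resection with no contribution from planning, or it could add minutes of viewing time.

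A report that follows the purpose and hypothesis as worded would credit planning with a benefit that may have arisen in theatre. With a null result, it would deny planning a benefit that viewing time may have offset.

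**Working it through.** The plan gives no figure on this point, so the check sets the sections side by side.

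**What the comparison estimates.** Write C for the mean operative time with CT/MRI only, P for the mean with the model used in planning only, and PI for the mean with the model used in planning and optionally in theatre. The trial has arms C and PI. Then

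PI − C = (P − C) + (PI − P).

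The left side is estimated by randomisation. The stated hypothesis concerns P − C. No arm delivers P, so there is one estimate for two unknown terms. Take the 10% difference that Section IV.e uses for power. An observed 10% reduction fits a planning effect of 10% with nothing from theatre, and fits equally a planning effect of 0 with 10% from theatre. An observed difference of 0 fits a 10% planning reduction cancelled by a 10% increase from viewing during surgery. The two terms are equal in none of these cases, and the trial data cannot choose between them.

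**When the planning reading would be safe.** PI − P is 0 if nobody views the model in theatre, or if such viewing has no net effect on the times. The documents assert neither. The target is 78 patients allocated 1:1, so 78 / 2 = 39 Intervention Cases, and the number with viewing in theatre can lie anywhere from 0 to 39. This is the logical range, not an estimate.

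**Whether the number would be known.** The places where it could be recorded are:

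- Exhibit A, covariates and endpoints: no item on viewing in theatre.
- First REDCap form (Section VII.a.i): identifiers and operation date only.
- Exhibit C: no such field, although its surgical technique list does include ultrasound and Firefly use.
- Post-operative survey (Section V.a): described as covering the primary endpoints and "the helpfulness of the VR Models during case planning".
- Surgeon experience survey (Exhibit B): no question about use during the operation.
- Coordinator contact (Sections VI.b.iii and VII.c.iv): viewing before the operation only.
- Analysis (Section IV.e): VR-aided against control, with a mixed model on the Exhibit A covariates. No term, tabulation or sensitivity analysis concerns use in theatre.

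**A side observation.** Section I.c describes the earlier comparison of 30 VR cases with 30 CT/MRI-only cases as planning use: "During the preoperative planning process for those cases, the surgeons viewed both the source CT scan as well as the virtual reality model". If that study supplied the pilot effect size of 0.44 in Section IV.d, which is an assumption because the documents do not say so, the sample size rests on a narrower intervention than the one delivered here.

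**The case against.** The strongest reply is that the option is open and deliberate. It is stated twice, and Section I.b cites a regulatory clearance for display during operations. Testing a technology as surgeons would use it is a legitimate pragmatic choice. Section I.b defines the comparison by whether the VR model was viewed, without limiting when, and Section IV.e compares VR-aided with control cases. Time spent viewing is then a real cost of the strategy and belongs in operative time. All of this stands. A reader might infer that the randomised comparison is invalid or biased, and the documents do not support that. The fault lies in the claim attached to the comparison.

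Three other strong readings also go too far.

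- A reader might infer that use in theatre will certainly go unrecorded. Exhibit C is headed as an example and also omits hilum dissection and mortality, which Exhibit A requires. Exhibit B is an initial list, and the full post-operative survey is not shown. Video is a data source too, though nothing says it would show model viewing. The supportable statement is that no listed field or described item captures it.
- A reader might infer from the clearance dates, August 2017 for planning and July 2018 for display in theatre, that the mix of use shifted during the trial. Neither the enrolment dates nor the date the option took effect is given, so this is conjecture.
- A reader might infer that recording use would let the planning effect be separated out. The choice to view in theatre comes after randomisation and probably depends on case difficulty, so comparing users with non-users would not be a randomised comparison.

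The hypothesis is also cautiously worded. That does not remove the mismatch, because the title and purpose name the planning stage as well.

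**Conclusion.** The concern holds as a mismatch between the claim and the intervention. The trial can support a conclusion about access to the VR model before and, at the surgeon's option, during the operation. It does not support a conclusion about preoperative planning alone, and nothing elsewhere in the plan repairs this.

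The size cannot be given in minutes. The share of Intervention Cases affected lies between 0 and 39 of 39, and no listed item would show where. The verdict assumes that the option is used in at least some cases and that such use can change operative times. If either fails, the planning reading would be correct, but the data as listed would not show it.

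The randomisation, comparator and sample size are not called into question on this ground. The point should be corrected, but it does not undermine the trial.

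**What to change.** 1. Restate the purpose (Section I.a), the hypothesis (Section I.b) and the eventual conclusion as the effect of access to the VR model before and, at the surgeon's option, during the operation. Align the title, or qualify it in the text.
2. Add one item to the Intervention Case data, in Exhibit C or the post-operative survey: VR model viewed during operation (y/n).
3. Report it descriptively, overall and by surgeon. With four surgeons and an even spread this is 39 / 4, or about 10 cases each, enough for a count but not for an effect estimate.
4. State in Section IV.e that this use is chosen after randomisation and will not be used to isolate a planning effect.

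On placement, Section IV.d keeps the video reviewers and the statistician blinded. An item completed only in Intervention Cases reveals the arm, so the surgeon survey is a better source than the video review. The item should be kept from the blinded staff until the main comparison has been run.

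The cost is some rewording and one yes/no answer on a survey already completed after every Intervention Case. The trial also gives up a claim specific to preoperative planning. No change to how surgeons use the model is needed or proposed.
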